8 STATISTICAL METHODS

8.1 General Statistical Conventions

All statistical procedures will be completed using SAS version 9.4 or higher.

Unless otherwise stated, all statistical testing will be two-sided and will be performed using a significance (alpha) level of [REDACTED]

Summaries for AS or nr-axSpA will be presented separately. Summary statistics will also be presented by treatment group. Continuous variables will be summarized using descriptive statistics, including number of subjects (n), mean, median, standard deviation (SD), minimum and maximum. One additional decimal point for mean and median and 2 additional decimal points for SD will be used.

For categorical variables, summaries will include counts of subjects and percentages. Percentages will be rounded to one decimal place.

Two-sided 95% confidence intervals (CI) will be provided when relevant.

For summary purposes, baseline will be defined as the last available value prior to the date of first IMP administration; all summaries will be presented by treatment group, unless otherwise specified.

For reporting purpose, summary tables for efficacy variables and safety variables will be displayed by nominal visit as appropriate. Unscheduled assessments will not be included in the summary tables, but will be displayed in data listings.

All subject data, including those derived, will be presented in individual subject data listings. Unless otherwise stated, unscheduled visit results will be included in date/time chronological order, within patient listings only. All listings will be sorted by cohort, treatment group, subject number, date/time and visit. The treatment group as well as patient's sex and age will be stated on each listing. Unless otherwise stated, data listings will be based on all randomized subjects.

The treatment groups will be displayed in the format below in tables including Part 1 only:

- [REDACTED] Tildrakizumab
- Placebo

The treatment groups will be displayed in the format below for tables including Parts 2 and/or 3 and all listings:

- [REDACTED] Tildrakizumab
- Placebo → [REDACTED] Tildrakizumab

Statistical Analysis Plan (SAP)

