### 9.1.3.5 Unscheduled Visits

An unscheduled visit is defined as any visit to the Investigator site outside of the Protocol-specified time points due to safety reasons or when a repeated measurement is required (e.g., obvious measurement errors, confirmation of out-of-range results), where the subject is seen by study personnel.

All unscheduled visits and assessments performed during the visits will be recorded in the subject's eCRF. During any unscheduled visits the Investigator will record any AEs and concomitant medications as well as performing any assessments or collecting samples deemed necessary at the discretion of the Investigator.

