8.7.2 Clinical laboratory evaluations

For the purposes of summarization in both the tables and listings, all laboratory values will be presented in SI units. If a lab value is reported using a nonnumeric qualifier e.g., less than (<) a certain value, or greater than (>) a certain value, the given numeric value will be used in the summary statistics, ignoring the nonnumeric qualifier.

Clinical laboratory parameters observed values and changes from Baseline will be summarized at each scheduled visit. Shift table from baseline to post-baseline in lab parameters for each treatment group during Part 1 will be displayed by visit.

Values outside the normal range will be categorized as H (above the normal range) or L (below the normal range) based on the laboratory's reference range and these will be flagged in the listings of individual subject data.

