8.7.3 Vital signs

Vital sign observed values and changes from Baseline will be summarized at each scheduled visit.

A listing of vital signs by subject will be produced.

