8.7.6 Assessment of Suicidal Ideation and Behavior

Subjects will be assessed for suicidal ideation and behavior at the Screening Visit using the Baseline (Lifetime) C-SSRS, and each subsequent visit using the C-SSRS Since Last Visit version.

The C-SSRS consists of 2 major aspects: Suicidal Ideation and Suicidal Behavior. Based on outcomes and data analyses suggested by the C-SSRS website, the following endpoints will be used to analyze C-SSRS data:

- Presence of Suicidal Ideation: Set to 1 if any ideation is present and 0 otherwise.
- Presence of Suicidal Behavior: Set to 1 if any type of suicidal behavior is present and 0 otherwise.
- Suicidal ideation score: Defined as the maximum suicidal ideation category (1-5) on the C-SSRS present at the assessment. A score of 0 is assigned if no ideation is present.

The number (%) of subjects with presence of suicidal ideation/behavior will be summarized at each assessment time. The C-SSRS data will be summarized using worst-case shift tables. Worst-case shift tables will be the cross tabulation of the Baseline result score with the worst-case result score during the treatment period.

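### As written, SAP 8.1 lets the C-SSRS worst-case table miss the worst score and leaves abnormalities seen only between visits out of the laboratory and ECG tables

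*SAP*

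**What the plan says.** SAP 8.1 sets the general convention: "summary tables for efficacy variables and safety variables will be displayed by nominal visit as appropriate". The next sentence reads: "Unscheduled assessments will not be included in the summary tables, but will be displayed in data listings". A later sentence in the same section, which allows for exceptions stated elsewhere, adds that "unscheduled visit results will be included in date/time chronological order, within patient listings only".

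Protocol 9.1.3.5 defines an unscheduled visit by its cause. It takes place "due to safety reasons or when a repeated measurement is required (e.g., obvious measurement errors, confirmation of out-of-range results", the last two items being the examples given. The investigator then records adverse events and concomitant medication and carries out whatever other assessments seem necessary. Everything done at the visit goes into the eCRF.

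The safety sections of the SAP then specify:

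- **Laboratory (8.7.2):** "Clinical laboratory parameters observed values and changes from Baseline will be summarized at each scheduled visit". Also: "Shift table from baseline to post-baseline in lab parameters for each treatment group during Part 1 will be displayed by visit".
- **Vital signs (8.7.3):** "Vital sign observed values and changes from Baseline will be summarized at each scheduled visit".
- **ECG (8.7.5):** parameters by scheduled visit, and a Part 1 shift table of the overall interpretation by visit and treatment group.
- **C-SSRS (8.7.6):** "Worst-case shift tables will be the cross tabulation of the Baseline result score with the worst-case result score during the treatment period".

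**The concern.** Leaving unscheduled values out of by-visit means is ordinary practice and is not the problem. The difficulty is that the convention is worded for summary tables in general, while the values it removes were collected for a safety reason or to check a doubtful result. A table meant to show the worst outcome should use all the data in its period, and those values are the ones most likely to matter.

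Two things are at stake. A reader of the study report may take the C-SSRS worst-case table at its name when a worse score exists in the database. And a reader of the laboratory or ECG shift tables may see a subject as normal at every visit when an abnormal value was recorded between two of them.

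**Working it through.** No arithmetic decides this point. The check is which records reach which table.

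**1. Table by table, applying 8.1 literally**

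| Data | Tables planned | Unscheduled post-baseline values included? | Worst post-baseline table? |
|---|---|---|---|
| Laboratory | By-visit summary; shift by visit, Part 1 | No | None |
| Vital signs | By-visit summary | No | None |
| ECG | By-visit summary; shift by visit, Part 1 | No | None |
| C-SSRS | Counts at each assessment time; worst-case shift | No exemption stated | Yes, but its input is unclear |
| AE and ECI | By event date and study part | Yes, if reported as an event | Not applicable |

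No laboratory or ECG section brings the unscheduled values back.

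**2. Could the next scheduled C-SSRS recover the score?** After Screening, SAP 8.7.6 uses the form that asks about the time since the previous visit. If the rater counts the unscheduled visit as that previous visit, the next scheduled form starts after it, and the earlier score exists only in the excluded record. If the rater goes back to the last scheduled visit, the next form can capture it. The SAP does not say which applies. A subject with no later scheduled assessment has no such form at all.

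**3. Could the event tables recover the finding?** In part.
- Under Protocol 12.1.4 a laboratory, vital sign or ECG abnormality is reported as an AE if it is clinically significant and also has associated symptoms, needs further testing or intervention, or leads to stopping or interrupting study drug.
- SAP 8.7.1 assigns events to study parts by date, so the type of visit does not matter.
- The same section counts unscheduled testing towards the liver-test ECI, and makes depression and suicidal ideation or behavior events ECIs.
- What remains uncovered is an abnormality that meets none of these criteria. For C-SSRS, an ECI count does not supply the shift in score that the worst-case table is meant to show.

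**4. Size.** The documents give no rate of unscheduled visits, nor of C-SSRS, laboratory or ECG assessments made at them. SAP 5 plans approximately 45 subjects per arm in each cohort. If all 45 are in the table, one subject placed in the wrong shift cell changes that arm's percentage by 1/45 = 2.2 percentage points. How many subjects would be affected is unknown.

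**The case against.** The best defence is that 8.1 is being read too widely. The exclusion follows directly on a sentence about by-visit display, so it may be meant only for by-visit tables. The sentence on listings allows for exceptions, and 8.7.6, by defining its table over the whole treatment period, may be one. This stands as a possible reading. It does not settle the matter, because 8.1 twice confines unscheduled results to listings and 8.7.6 says nothing about them. The programmer has to choose.

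The existing safeguards also stand: every value is listed, out-of-range laboratory values are flagged there, and significant findings become AEs or ECIs. They narrow the gap without closing it.

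Three stronger readings are tempting, and the documents do not support them.

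- **That every unscheduled value is lost from every table.** Baseline is the latest value before first dosing and is not restricted to scheduled visits, so an unscheduled pre-dose value can enter change and shift tables.
- **That the tables would keep known measurement errors.** The visible text has no rule for replacing a value by its repeat, but silence does not show that a documented error would survive data cleaning into the locked database. SAP 7.2.1 also refers to details in a place that is blacked out.
- **That the safety summaries as a whole are biased toward normal.** When a repeat is taken to confirm an out-of-range scheduled value, the abnormal value stays in the table and the repeat is dropped. A retained error can push a summary either way. The net direction is unknown.

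**Conclusion.** The point holds in a limited form. Followed as written, the C-SSRS worst-case table can omit the worst score, and laboratory and ECG abnormalities found only at unscheduled visits do not appear in the tables for those data. Outside Part 1 no laboratory or ECG shift table is planned at all.

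The conclusion assumes that 8.1 is applied literally, that no exemption sits in blacked-out text or in the separate table templates, and that some subjects have these assessments at unscheduled visits. Safety is descriptive with no testing, and nothing here shows an effect on the primary ASAS20 analysis. This is a gap in safety reporting that is cheap to close; it is not a threat to the trial's main result.

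**What to change.** 1. In SAP 8.1, limit the exclusion of unscheduled assessments to by-visit descriptive tables.
2. In SAP 8.7.6, state that the worst-case shift table uses all post-baseline C-SSRS assessments in the treatment period, including unscheduled ones.
3. In SAP 8.7.2 and 8.7.5, add a shift table from baseline to worst post-baseline value for each study part, including unscheduled values.

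Optionally, add a sentence that a scheduled value documented as a measurement error is replaced by its repeat. This is a clarification only.

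The data are already in the eCRF, so the cost is SAP wording and a few extra tables. The downside is a slightly higher reported frequency of abnormalities, in both arms. If the SAP is no longer open to revision, its section 1 allows departures to be described and justified in the study report, and the same tables can be added there.

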8.2 Protocol deviations

Population membership details will be listed, including reason for exclusion from each population.

All major protocol deviations identified will be summarized by treatment group and overall.

A listing will include the inclusion/exclusion criteria violated at Screening and at Baseline Visits as well as other protocol deviations identified based on data recorded on the eCRF and/or protocol deviation Logs from ICON Medical.

8.3 Subject disposition

The number of subjects in the following categories will be summarized overall and by treatment group:

- Randomized
- Full Analysis Set (FAS)
- Per Protocol Analysis Set (PPAS)
- Safety Analysis Set

The number and percentage (based on FAS) of subjects in each of the following disposition categories will be summarized overall and by treatment group:

- Completed treatment at Parts 1 and 2
- Prematurely discontinued the treatment and the reasons for discontinuation
- Completed study (i.e., completed the wash-out period)
- Prematurely discontinued the study and the reason for discontinuation

A listing will be provided for subjects who discontinued treatment or who discontinued study with reasons for discontinuation.

8.4 Demographics and baseline characteristics

The demographics and baseline characteristics, medical history, prior and concomitant medications will be summarized by treatment group and overall for the FAS. Individual subject listings will be provided to support the summary tables.

8.4.1 Demographics

Age (years), height (cm), weight (kg), and other continuous demographic variables at Screening will be summarized descriptively. Gender, primary race, ethnicity, and other categorical variables will be summarized using FAS.

Year of birth, age, gender, race, ethnicity, height and weight will be listed as part of demographic listing.

Statistical Analysis Plan (SAP)

8.4.2 Baseline characteristics

Tender joint counts [REDACTED] swollen joint counts [REDACTED] PGA of disease activity, PtGA of disease activity, total back pain, and nocturnal pain, MASES, ASQoL, SF-36, BASDAI, BASMI, BASFI, FACIT, SPARCC MRI Index of Disease Activity Score of the SI Joints and Spine, Modified Berlin ASspiMRI, ASDAS-CRP, ASDAS-ESR, hsCRP, ESR at baseline will be summarized. Rheumatoid factor and HLA B-27 at screening will be summarized as well.

8.4.3 Medical history

A summary of medical history will be presented by system organ class (SOC) and preferred term (PT) using the most recently available version of the Medical Dictionary for Regulatory Affairs® (MedDRA). A listing of medical history will be provided as well.

Quantiferon testing and chest X-ray results at screening will be summarized using frequency counts for FAS.

8.4.4 Prior and concomitant medications

Medications used in this study will be coded by using the World Health Organization Drug Dictionary and categorized as the following:

Prior medications and concomitant medications will be summarized descriptively using frequency tables by ATC class and preferred name by treatment group on the Safety Analysis Set. Prior medications are those with a stop date before the first dose of study drug, and concomitant medications are those with a stop date on or after the first dose of study drug or ongoing.

Details for imputing missing or partial start and/or stop dates of medication are described in [REDACTED]

Prior biologic and prior anti-TNF medications will be summarized in a separate table.

8.5 Extent of exposure

8.5.1 Treatment Duration

Duration of study drug exposure (in days) will be calculated as: last dose date – first dose date + 1 day, regardless of study drug interruption.

Study drug exposure will be summarised by treatment group on the Safety Analysis Set using descriptive statistics.

Exposure to randomized study drug will also be categorised in intervals [REDACTED]

[REDACTED] and summarized by treatment group.

8.5.2 Treatment Compliance

Study drug compliance will be calculated as: [REDACTED] total number of doses administered /total

Statistical Analysis Plan (SAP)

number of doses planned to be administered during the study drug exposure period. In case only one syringe among the two is administered at a visit, the number of doses will be counted as [REDACTED]. If both syringes are administered at a visit, the number of doses will be counted as 1. The total number of doses planned will count Weeks 0, 4, 8, 12, 16, 20, 24, 28, 32, 36, 40, 44, and 48 if a subject completes Part 1 and Part 2. If a subject discontinues treatment early, the total number of doses will be counted from Week 0 until the last dose before discontinuation.

Study drug compliance will be summarized by treatment group by the number of subjects (n), mean, SD, median, min, and max. They will also be summarized in categories [REDACTED] and [REDACTED] using frequency tables.

Study drug compliance summaries will be based on the Safety Analysis Set.

8.6 Efficacy analyses

8.6.1 Analysis methods

Analysis of proportions

The Cochran-Mantel-Haenszel (CMH) test, incorporating prior anti-TNF use as a stratification factor, will be used to compare response rates of response-type variables between the 200 mg tildrakizumab and placebo within AS and nr-axSpA separately. In addition, the Mantel-Haenszel common risk (the response rate) difference between 200 mg tildrakizumab and placebo and the 95% confidence interval (CI) will be estimated. Should assumptions per the Mantel-Fleiss criterion not be satisfied, the comparison will be based on a Fisher's exact test after collapsing across levels of the stratification factor. In this case, the response rate difference and CI will be based on a normal approximation without considering stratification.

Mixed model repeated measures analysis of continuous endpoints

A mixed model repeated measure (MMRM) analysis will be performed. The SAS procedure PROC MIXED will be used. The preferred model will include the fixed categorical effects of treatment, visit, treatment-by-visit interaction, and prior TNF use (yes/no), as well as the continuous fixed covariate of baseline value. An unstructured matrix for the within-subject error variance-covariance will be used. The denominator degrees of freedom will be calculated according to the Kenward-Roger method.

In case of non-convergence with the unstructured matrix, other within-subject error variance-covariance matrices, such compound symmetry (CS), will be considered.

The model will provide least-squares mean estimates, standard errors, two-sided 95% confidence intervals and p-values (where applicable) for mean change at all time points between treatments (tildrakizumab vs. placebo).

Statistical Analysis Plan (SAP)

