Name of Sponsor/Company: Sun Pharma Global FZE	Individual Study Table Referring to Part of the Dossier:	(For National Authority Use Only)
Name of Product: Tildrakizumab	Volume:	
Name of Active Ingredient: Tildrakizumab	Page:	

**Statistical Methods:**Sample Size Calculation

In each subject cohort (AS and nr-axSpA), approximately [ ] subjects will be randomized per arm in a [ ] ratio to tildrakizumab [ ] or placebo, stratified by anti-TNF use (yes/no). This sample size achieves [ ] power (accounting for futility assessment) to detect a treatment effect in ASAS20 at [ ] of [ ] (placebo ASAS20 = [ ]; tildrakizumab ASAS20 = [ ]). The test statistic used is the [ ] Cochran-Mantel-Haenszel (CMH) test at the [ ] significance level. A [ ] drop-out rate has been assumed.

An interim analysis will be performed for futility assessment after data at Week 16 from 30 randomized subjects become available. Futility assessment will be based on a futility threshold of 12% (difference between response rates on active arm and placebo) at Week 16.

Statistical Analysis:

The primary efficacy analysis population will be the Full Analysis Set (FAS) defined as all randomized subjects who have received at least [ ] of IMP. The primary analysis will be based on the CMH test, incorporating anti-TNF use as a stratification factor, to compare the response rates for the primary endpoint ASAS20 [ ] between placebo and the active dose group within AS and nr-axSpA separately. In addition, the Mantel-Haenszel common risk (the response rate) difference between placebo and the active dose arm and corresponding confidence interval (CI) will be estimated. Should CMH assumptions per the Mantel-Fleiss criterion not be satisfied, the treatment comparison will be based on a Chi-square tests following collapsing of the strata. Early withdrawals or any other subjects with incomplete data at [ ] will be classified as non-responders for the primary endpoint ASAS20. Subjects who fail to show minimal response to treatment (defined as [ ] from Baseline in pain [assessed by Total Back Pain [ ]] and inflammation [assessed using the last [ ] assessments in the BASDAI]) at Week 16 may have their background medications adjusted according to the maximum permitted daily dose [ ] and continue in the study. Any subject requiring these adjustments will be counted as a non-responder for the primary analysis.

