3.2 Randomization and blinding

3.2.1 Randomization

A randomization schedule will be computer-generated before the start of the study. After all screening procedures are performed and results of screening tests are available (i.e., between the Screening visit and [REDACTED]), [REDACTED] will be activated in the interactive voice recognition system (IVRS), and assigned randomly on a [REDACTED] basis to the following treatment groups for cohorts of [REDACTED], respectively:

- A: [REDACTED] tildrakizumab, [REDACTED]
- B: Placebo, administered by [REDACTED]
[REDACTED]

Randomization will be performed by the [REDACTED]. Subjects will be stratified by prior anti-tumor-necrosis factor (anti-TNF) use (yes/no). Subjects with prior anti-TNF use will be capped [REDACTED] [REDACTED] of the total number of subjects.

Statistical Analysis Plan (SAP)

[REDACTED] (Stage 1) subjects will begin upon study approval; recruitment for [REDACTED] (Stage 2) subjects will begin only upon written notification by the Sponsor to the Competent Authorities and Investigators.

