5 SAMPLE SIZE AND POWER

In each subject cohort (AS and nr-axSpA), approximately 45 subjects will be randomized per arm in a 1:1 ratio to tildrakizumab 200 mg or placebo and will be stratified by anti-TNF use (yes/no). This sample size achieves 80% power (accounting for futility assessment) to detect a treatment effect in ASAS20 at [REDACTED] (placebo ASAS20 = [REDACTED]; tildrakizumab ASAS20 = [REDACTED]). The test statistic used is the [REDACTED] Cochran-Mantel-Haenszel (CMH) test at the [REDACTED] significance level. A [REDACTED] drop-out rate has been assumed.

Statistical Analysis Plan (SAP)

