8.6.2 Analysis of primary efficacy endpoint

The primary efficacy variable is ASAS20 at [REDACTED] ASAS20 will be analysed with CMH test as described in [REDACTED] for AS and nr-axSpA cohorts separately. Early withdrawals and any subjects with ASAS20 undeterminable at [REDACTED] will be classified as non-responders. Subjects who fail to show minimal response to treatment (defined as [REDACTED] improvement from Baseline in total back pain or inflammation) at [REDACTED] may have their background medications adjusted according to the maximum permitted daily dose described in the protocol and continue in the study. Any subject requiring these adjustments will be counted as a non-responder for the primary analysis.

The sample SAS codes are:

[REDACTED]
[REDACTED]
[REDACTED]

To assess the robustness of the primary efficacy analysis, sensitivity analysis will be repeated with the PPAS.

Subgroup analysis will be performed for each of the following subgroup variables:

- Prior anti-TNF use (Yes/No)
- Baseline weight (≤ 90 kg, > 90 kg)
- Age (< 65 , ≥ 65)
- Gender
- Methotrexate use (Yes/No)

The sample SAS codes for anti_TNF subgroup analysis are:

[REDACTED]
[REDACTED]
[REDACTED]
[REDACTED]
[REDACTED]
[REDACTED]

Estimates of the difference between the treatment groups, along with the [REDACTED] (but no p-value needed), will be presented for each defined category of each subgroup variable.

Statistical Analysis Plan (SAP)

If sample size for a category of a subgroup factor is too small, the analysis for that subgroup may not be performed.

The primary purpose of the subgroup analyses is to check for consistency of results across factors of interest.

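### In the sparse-data fallback the SAP switches to Fisher's exact test but keeps an unstratified normal-approximation interval, which can exclude zero when the test is not significant and usually covers slightly below 95%

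*SAP*

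**What the plan says.** SAP 8.6.1 (Analysis of proportions) compares response rates by CMH stratified on prior anti-TNF use, with a Mantel-Haenszel common risk difference and 95% CI. The fallback applies under this condition: "Should assumptions per the Mantel-Fleiss criterion not be satisfied". Then "the comparison will be based on a Fisher's exact test after collapsing across levels of the stratification factor", and for estimation: "In this case, the response rate difference and CI will be based on a normal approximation without considering stratification". The methods summary placed before the SAP (16.1.9) repeats the rule.

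SAP 8.6.2 applies the method to the primary endpoint, ASAS20, in each cohort. SAP 8.6.3 applies it to ASAS40 at Week 24. For subgroups, SAP 8.6.2 says that treatment differences with an interval "will be presented for each defined category of each subgroup variable", without p-values. The name of that interval and the code are blacked out, and a category may be skipped if it is too small.

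The protocol synopsis (Statistical Methods) names a different fallback test: "the treatment comparison will be based on a Chi-square tests following collapsing of the strata". Protocol 13.5.3 has the same unstratified normal-approximation interval.

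**The concern.** The Mantel-Fleiss criterion asks whether there are enough events for a large-sample test. When the answer is no, the SAP makes the test exact but leaves the interval on a large-sample formula. Two things can follow. The interval may cover less than its nominal 95%. It may also exclude zero while the reported p-value exceeds 0.05, so that one comparison carries two conclusions, and the SAP has no rule on which one governs.

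**Working it through.** **Inputs.** From SAP 5: "approximately 45 subjects will be randomized per arm in a 1:1 ratio", in each cohort. From SAP 8.1: two-sided testing and 95% intervals. Blacked out, hence assumed: the test level (two-sided 0.05, to match the 95% CI) and the response rates (scanned). The interval is taken as uncorrected unless stated.

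**The plan's own figure.** The 80% power cannot be reproduced, because rates, level and drop-out are blacked out. Solving backwards, 45 per arm gives 80% power for a difference of 0.276 to 0.291 (placebo 20-40%, two-sided 0.05, no drop-out).

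**When the fallback is reached.** Mantel-Fleiss requires min(ΣE − ΣL, ΣU − ΣE) ≥ 5, where E is the expected count in one cell and L and U are its smallest and largest possible values. For a collapsed 45 v 45 table with S responders (S ≤ 45), E = S/2, L = 0 and U = S, so the criterion is S/2 ≥ 5. It fails with 9 or fewer responders, or by symmetry 9 or fewer non-responders, out of 90. A two-stratum simulation with 10-40% prior anti-TNF users gives almost the same frequencies.

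| Rates (45 per arm) | P(fallback) |
|---|---|
| 30% or more in both arms (e.g. 30 v 30, 50 v 30) | about 0 |
| 20 v 20 | 0.9% |
| 20 v 10 | 11% |
| 15 v 5 | 59% |
| 12 v 2 | 91% |
| 5 v 5 | 98.6% |

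At the design effect with 20% on placebo, expected responders are 45 × 0.20 + 45 × (0.20 + 0.276) = 30.4, far above 9.

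**A table in the fallback region: 4/45 v 0/45.**
- Fisher, two-sided: 2 × C(45,4)/C(90,4) = 2 × 148,995/2,555,190 = 0.117.
- Difference: 4/45 = 0.0889. SE = √(0.0889 × 0.9111/45 + 0) = 0.0424; the arm with no responders contributes no variance.
- Interval: 0.0889 ± 1.96 × 0.0424 = 0.006 to 0.172, which excludes zero.

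Three more tables behave in the same way:
- 5 v 0: p=0.056, CI 0.019 to 0.203.
- 6 v 1: p=0.110, CI 0.003 to 0.219.
- 7 v 1: p=0.058, CI 0.019 to 0.248.

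With arms exchanged and responders exchanged for non-responders, these four make 4 × 2 × 2 = 16 conflicting fallback tables at 45 v 45. In all 16 the interval excludes zero and Fisher does not reject.

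**How often, and coverage.** All pairs of binomial outcomes were enumerated and weighted by their probabilities.

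| Case | Coverage, uncorrected | Coverage, Newcombe | Conflict given fallback, uncorrected | Conflict given fallback, Newcombe |
|---|---|---|---|---|
| 45 per arm, 12 v 2% | 92.4% | 97.3% | 27.4% | 13.3% |
| 45 per arm, 15 v 5% | 94.1% | 96.5% | 17.1% | 8.8% |
| 6 per arm, 40 v 20% | 87% | 94.7% | – | – |

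Over 90 rate pairs of 2-20% at 45 per arm where the fallback is more likely than not, uncorrected coverage has minimum 87.8%, median 94.0% and maximum 99.0%, and is below 95% in 83% of pairs. Conflict given the fallback runs from 1% to 28%, median 10.5%. At 15 per arm the median coverage is 91.1%.

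**Sensitivity to exact balance.** With arms of 44 and 46, conflict given the fallback at 12 v 2% is 13% if the higher rate is in the smaller arm and 28% if it is in the larger.

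**Sensitivity to a continuity correction.** For 4 v 0, widening each side by (1/45 + 1/45)/2 = 0.022 gives about −0.016 to 0.194, which includes zero. Over the same grid, corrected coverage is at least 95.3% with no conflicts at 45 v 45, and at least 95.1% with 6 conflicting tables at 44 v 46.

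**The case against.** Much of the case on the other side stands.

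- The primary result is barely exposed, since ASAS20 at plausible rates does not reach the fallback. Most other response endpoints are descriptive under SAP 8.6.4, although the methods summary before the SAP says that they were analysed similarly.
- A reader might infer that the interval always under-covers. It does not: uncorrected coverage at 45 per arm is 95.1% at 5 v 5% and 99.0% at 2 v 2%, and a continuity correction, if the hidden code has one, removes the shortfall at 45 v 45 and 44 v 46.
- A reader might infer that interval and p-value point in opposite directions. They do not: the estimate has one sign, and the disagreement is only about whether zero is excluded. The reported test is the more cautious of the two, so the test itself makes no false claim.
- A reader might infer an unlisted change from chi-square to Fisher, since SAP 10 mentions only the dropped PK and ADA analyses. The documents cannot establish this. The protocol supplied is dated 14 June 2017, whereas the SAP is written to V3.0 of 19 March 2018, whose fallback is not visible. Protocol 13.5.3 blacks out the test name.
- A reader might infer that the fallback test must be stratified. Collapsing is pre-specified in both documents and is a recognised trade-off when data are sparse.
- In subgroup tables no p-value is shown, so no contradiction can arise there, and it is unknown whether their interval is a normal approximation.
- A score interval does not remove the conflict. Over all samples at 12 v 2%, disagreement with Fisher is 26.3% for the uncorrected interval, 20.1% for Miettinen-Nurminen and 12.2% for Newcombe.

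None of this explains why an approximation judged inadequate for the test should serve for the interval.

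**Conclusion.** The point holds as a minor improvement to the fallback. Fisher's test is paired with an interval that does not match it. At 45 per arm the uncorrected interval usually covers slightly below 95%, with larger shortfalls in small samples. Given the fallback, it excludes zero against a non-significant Fisher test in about 17% of samples at 15 v 5% and 27% at 12 v 2%. These figures assume two-sided 0.05, the stated rates, equal arms and no continuity correction.

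It matters for ASAS40 at Week 24 if response is low, or for a cohort smaller than planned; SAP 10 records that the study was terminated. It does not threaten full-cohort ASAS20 at rates of 30% or more.

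**What to change.** In SAP 8.6.1, replace the normal-approximation interval in the fallback with one matched to the reported test, in either of two ways:

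- Report an exact interval beside the exact test, either exact unconditional or obtained by inverting the reported test. Only inversion of the reported test guarantees agreement with it.
- Report a Miettinen-Nurminen or Newcombe score interval, and state that the test governs significance and that a score interval reduces but does not remove conflict with Fisher.

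Use the same interval in the subgroup tables of SAP 8.6.2 if they now use a normal approximation. If the normal approximation is kept anywhere, state whether it is continuity-corrected.

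The cost is a few lines of SAP wording and slightly wider intervals. Sample size, data collection and the CMH analysis do not change.
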